**Other Objective 2.4.2:**

Analyses to address this objective will include women in Cohort 1 and women in Cohort 2 in the analysis sample. Estimates of the proportion of women (at each visit) reporting condomless vaginal or anal sex at each visit that it is measured, and the proportion of visits with condomless vaginal or anal sex during pregnancy and during the postpartum period will be compared between Cohort 1 and Cohort 2 using chi square tests. To evaluate the association of Cohort (Cohort 1 vs. Cohort 2) with sexual risk behavior, GEE models will be fit, including adjustment for sociodemographic and behavioral factors that could confound the association of Cohort with risky sexual behavior. Cox regression methods will be used to estimate and compare the incidence rates of STIs in the antepartum period, the postpartum period, and throughout the study, among women with no STIs at enrollment in Cohort 1 and Cohort 2, adjusting for baseline confounders. Cox regression methods will be used to estimate and compare HIV incidence rates in pregnant and breastfeeding women who have initiated PrEP, in comparison to women who decline PrEP during the antenatal period.

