### 9.2.4 Sample Size and Accrual

The PrEP Comparison Component will enroll a total of 350 (233 in Cohort 1 and 117 in Cohort 2) women over a 12-month period. Women will be followed through 26 weeks postpartum. Expected duration of follow-up for a given maternal participant is between 7 and 12 months depending on the gestational age of the pregnancy at enrollment. The following sample size and power calculations assume a final analysis sample of 300 women (200 in Cohort 1 and 100 in Cohort 2). The primary reason for the 2:1 enrollment into the two cohorts was to balance the need for a “No PrEP” comparison group (to provide the background rates for safety outcome measures) with the need for a large enough PrEP group to examine outcomes that would be restricted to women in that group (Adherence). To achieve this sample size at the analysis phase, this study will enroll ~350 women to accommodate a decrease of ~15% due to maternal attrition.

**Table 8** shows the expected precision of a range of PrEP adherence estimates across different sample sizes in Cohort 1. For example, with a sample size of 200 women in Cohort 1, the width of the 95% confidence interval for an estimated adherence rate of 75% is 13%.

**Table 8: Precision (shown as 2-sided 95% confidence intervals) of different estimates of the proportion with good adherence (for illustration, defined as meeting or exceeding the threshold corresponding to protective drug levels of TFV-DP) at different sample sizes for Cohort 1.**

% Adherent	Sample Size in Cohort 1			
	150	200	250	300
50	42-58%	43-57%	44-56%	44-56%
60	52-68%	53-67%	54-66%	54-66%
65	57-73%	58-72%	59-71%	59-70%
70	62-77%	63-76%	64-76%	65-75%
75	67-82%	68-81%	69-80%	70-80%
80	73-82%	74-85%	75-85%	75-84%

**Table 9** below shows the precision of estimates of safety outcomes (e.g. preterm birth) expected with a range of event rates and a sample size of 200 women in Cohort 1 and 100 women in Cohort 2. It is expected that the rates of these outcomes will be low particularly since this is a young group of healthy HIV uninfected women. To that end, a range of AE rates with corresponding confidence intervals is included in the protocol.

**Table 9: 95% Confidence Intervals for different possible event rates of safety outcomes in Cohort 1 (n=200) and Cohort 2 (n=100)**

Event Rate	95% Confidence Interval	95% Confidence Interval
	Cohort 1 (n=200)	Cohort 2 (n=100)
0.5%	(0, 2.8)	(0, 3.6)
2.0%	(0.5, 5.0)	(0.2, 7.0)
4.0%	(1.7, 7.7)	(1.1, 9.9)

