10.0%	(6.2, 15.0)	(4.9, 17.6)
15.0%	(10.4, 20.7)	(8.6, 23.5)
20.0%	(14.7, 26.2)	(12.7, 29.2)
30.0%	(23.7, 36.9)	(21.2, 40.0)

The study allows adequate power to detect moderate cohort differences from 8.5% to 16%, depending on the true background rate of the event, as summarized below in **Table 10**. The table shows minimum detectable differences in safety outcomes between Cohort 1 and Cohort 2 which could be achieved with 80% power and alpha=0.05. For example, based on a sample size of 200 in Cohort 1, and assuming a 2:1 enrollment among women agreeing to and declining PrEP, differences of at least 13% will be detectable between the two cohorts in the proportion of maternal adverse events for events with a 10% background rate (10% in Cohort 2, 23% in Cohort 1).

**Table 10: Minimum detectable differences in safety outcomes based on evaluable sample size of 300 for Cohort 1(n=200) and Cohort 2 (n=100), 80% power, alpha=0.05**

% with event in Cohort 2 (N=100)	% with event in Cohort 1 (N=200)	Odds Ratio
2%	10.5%	5.8
5%	15.6%	3.5
10%	23%	2.67
15%	29%	2.36
20%	35%	2.19
25%	41%	2.10

To address primary objective 2.3.2, the mean bone mineral content of infants at birth and at age 26 weeks will be estimated and differences in mean bone mineral content between infants in Cohort 1 and Cohort 2 will be evaluated using two sample t tests. **Table 11** shows the statistical

power the study would have to detect a range of estimated differences in means. For example, with a sample size of 200 in Cohort 1 and 100 in Cohort 2 this study will be able to detect differences in mean bone mineral content of at least 0.35 SD with 80% power. Based on the SMARTT study in the U.S., assuming a standard deviation of 16.6 (77) this would be equivalent to a difference in means of 5.81g. Assuming a standard deviation of 14.9 found in the P1084s study (79) this would be equivalent to a difference in means of 5.22 g.

**Table 11: Estimated Power to Detect the Mean Differences in Infant Growth Outcomes Infant DXA, Whole Body Bone Mineral Content (BMC) (g) at Birth (Mean=63.8, SD=16.6)\*\***

Difference to be Detected	Effect Size (SD)	Power (based on sample sizes*)		
		N1=200 N2=100	N1=180 N2=90	N1=160 N2=80
4% (of 63.8)	2.55 (16.6)	24%	22%	20%
5%	3.19	35%	32%	29%
6%	3.83	47%	43%	39%
7%	4.47	59%	55%	50%
8%	5.10	71%	66%	61%
9%	5.74	80%	76%	71%
10%	6.38	88%	84%	80%
0.25*SD	4.15	53%	49%	44%
0.30*SD	4.98	68%	64%	59%
0.35*SD	5.81	81%	77%	72%
0.40*SD	6.64	90%	87%	83%
0.45*SD	7.47	96%	94%	91%

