### Primary Objective 2.3.1:

- Women in Cohort 1 will comprise the analysis sample. A binary indicator, “optimal adherence” will be created, as defined above as TFV-DP levels in DBS meeting or exceeding the threshold determined in the PK Component as corresponding to protective levels of PrEP (24). At each visit that TFV-DP levels are obtained (see [Appendix IIA](#)), the proportion of women with optimal adherence will be calculated based on their TFV-DP levels at each visit. The proportion of visits with optimal adherence in the pregnancy vs. postpartum periods will be calculated and compared.
- Exploratory analyses identifying baseline and time-varying predictors of optimal adherence will be conducted with multivariable regression models using generalized estimating equations with a logistic link (to account for repeated measures across time for each participant).
- Adherence (as measured in TFV-DP levels) will also be summarized as a continuous outcome (median, IQR and mean [SD]) at each time point noted above when drug levels are measured, and “average” adherence across pregnancy and postpartum periods, will be calculated, using generalized estimating equations. We will focus on periods during which the participant has formally elected to be on PrEP. If a woman elects to formally stop PrEP (by notifying study personnel), periods of being formally off study drug will not be considered in adherence calculations.
- Other approaches to summarizing the adherence outcome will be considered. This includes an ordinal variable with categories corresponding to different dosing levels. For this type of outcome, at each visit that drug levels are measured in DBS, descriptive analyses will summarize the proportion of women in each adherence category, refer to categories discussed in [Section 9.1.6](#).

- Baseline characteristics, and patterns of adherence and duration on PrEP will be summarized separately for women in Cohort 2 who later decide to initiate PrEP using the approaches outlined above.
- The following additional descriptive statistics will be calculated: The proportion of women a) with at least one visit with TFV-DP levels corresponding to optimal adherence, b) who had TFV-DP levels corresponding to optimal adherence at all visits, c) who had no detectable TFV-DP levels at any visit.

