 If the participant has not delivered at 12 weeks of follow-up, participants may choose to continue in follow-up until delivery, refer to [Section 5.1.2.1](#)

 If within the window of one of the weekly visits, visits may be combined.

 Questionnaire is done at Week 12 visit only; questionnaire is not required at early D/C.

 If positive refer to [Section 6.3](#) and [Appendix IID](#) for additional procedures.

 Store plasma for HIV drug resistance testing at all visits indicated EXCEPT Screening.

 Blood collected for other tests will be used for the rapid HIV test. Collection of additional blood is not required.

 Urine (5mL) or blood (1mL) tests are acceptable. The total blood volume shown above accommodates collection of 1mL of blood, if needed.

## Appendix IB (Schedule of Evaluations): Infant PK Component Group 1

INFANT PROCEDURES: Group 1	Birth	PP Wk 6	Early D/C
Medical and Medications History	X	X	X
Physical Examination	X	X	X
Infant Feeding History	X	X	X
LABORATORY EVALUATIONS			
Creatinine	1mL	1mL	1mL
TFV-DP level (DBS)	0.5mL		
Total maximum blood volume	1.5mL	1mL	1mL

## Appendix IC (Schedule of Evaluations): Infant PK Component Group 2

INFANT PROCEDURES: Group 2	Entry (Day 0)	Wk 6	Wk 12 and Early D/C
Medical and Medications History	X	X	X
Physical Examination	X	X	X
Infant Feeding History	X	X	X
LABORATORY EVALUATIONS			
Creatinine	1mL	1mL	1mL
TFV-DP level (DBS)	0.5mL	0.5mL	
Total maximum blood volume	1.5mL	1.5mL	1mL

## Appendix IIA (Schedule of Evaluations): Maternal PrEP Comparison Component: Cohort 1, Cohort 2/Step 2

MATERNAL PROCEDURES:	SCR	Entry	Wk 4	Wk 8	Wk 12	Wk 24	Wk 36	L&D	PP Wk 6	PP Wk 14	PP Wk 26 / Exit and Early D/C	Interim Visit
Informed Consent	X											
Medical and Drug History	X	X	X	X	X	X	X	X	X	X	X	
Physical Examination	X	X	X	X	X	X	X	X	X	X	X	
Study drug dispensing		X	X	X	X	X	X	X	X	X		
Assess for social harms			X	X	X	X	X	X	X	X	X	
iNSC	X	X										X
iNSC with drug level feedback			X	X	X	X	X	X	X	X		
CASI evaluations and COVID-19 questionnaire		X	X	X	X	X	X			X	X 	
Qualitative IDI							X				X	
HIV RNA  ; store plasma for HIV drug resistance testing 	4mL	6mL	6mL	6mL	6mL	6mL	6mL	6mL	6mL	6mL	6mL	
Rapid HIV 	X	X	X	X	X	X	X	X	X	X	X	
TFV-DP level (DBS)		4mL	4mL	4mL	4mL	4mL	4mL	4mL	4mL	4mL	4mL	
Complete Blood Count	3mL										3mL	

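### Other Objective 2.4.2: the chi-square tests on pooled visits ignore repeated visits by the same woman, so their p-values are too small; the planned GEE should carry the inference

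*Protocol*

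**What the plan says.** Section 9.2.6 of the protocol, under Other Objective 2.4.2, sets out three analyses of condomless sex.

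- **By visit.** "Estimates of the proportion of women (at each visit) reporting condomless vaginal or anal sex at each visit that it is measured" are compared between cohorts by chi-square. Each woman counts once per test.
- **By period.** In the same sentence, the proportions of visits with condomless sex "during pregnancy and during the postpartum period will be compared between Cohort 1 and Cohort 2 using chi square tests". The unit here is the visit. No allowance for repeated visits is stated.
- **By model.** The next sentence reads "To evaluate the association of Cohort (Cohort 1 vs. Cohort 2) with sexual risk behavior, GEE models will be fit", with adjustment for sociodemographic and behavioral confounders. It names no separate contrast for pregnancy or postpartum, and no working correlation or variance estimator.

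Nothing says which of these is the inferential analysis. Under Primary Objective 2.3.1 the same section explains that GEE is used "to account for repeated measures across time for each participant".

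Sexual behavior is a CASI domain (Section 6.16.2.2). The row "CASI evaluations and COVID-19 questionnaire" in Appendix IIA is marked at Entry, Weeks 4, 8, 12, 24 and 36, and postpartum Weeks 14 and 26. It is not marked at Labor and Delivery or postpartum Week 6. SAP Section 1.1 leaves non-primary objectives to a separate SAP, which is not among the documents.

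**The concern.** A chi-square test on pooled visits takes every visit as an independent observation. A woman belongs to one cohort and reports on her own behavior several times, so her reports are very likely to be positively correlated. Pooling them overstates the information, and the test can reject because women differ from one another when the cohorts do not.

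Section 1.2 names behavioral disinhibition as a risk that may accompany PrEP, and Objective 2.4.2 is where cohort differences in sexual risk behavior are examined. An unadjusted p-value that is too small could be reported as risk compensation, or as its opposite. It could also disagree with the GEE on the same question, with no stated rule for which one counts.

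**Working it through.** **Plan's own figure.** None is given for Objective 2.4.2: no power, error rate or correlation. As a check on cohort sizes and alpha, take the Table 10 example, a difference "which could be achieved with 80% power and alpha=0.05": 10% of 100 women against 23% of 200.

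- Pooled proportion = (10 + 46)/300 = 0.187.
- Null SE = √(0.187 × 0.813 × (1/100 + 1/200)) = 0.0477.
- Alternative SE = √(0.10 × 0.90/100 + 0.23 × 0.77/200) = 0.0423.
- Power = Φ((0.13 − 1.96 × 0.0477)/0.0423) = 80.6%, which agrees with the plan.

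**Inputs**
- 200 and 100 women (Section 9.2.4).
- Two-sided alpha of 0.05. The protocol states 0.05 for the safety comparisons, so its use here is an assumption.
- Pregnancy visits per woman (m): Entry plus Weeks 4, 8 and 12, with Weeks 24 and 36 only for women enrolled before about 20 weeks (Section 6.2.1.3). About 3 to 5 is realistic. A sixth is nearly unreachable: Week 36 is Day 252 ± 14, so at the earliest 238 days = 34 weeks after entry. With delivery at 40 weeks (assumed), entry would have to be at about 40 − 34 = 6 weeks.
- Postpartum visits: m = 2.
- Within-woman correlation (ICC): assumed, 0.1 to 0.7.
- Sexual behavior items are assumed to be asked at every CASI. The extra CASI at Step Change visits is not counted.

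**Formula.** Design effect DE = 1 + (m − 1) × ICC. Actual alpha of the unadjusted test = 2 × (1 − Φ(1.96/√DE)). For m = 4 and ICC = 0.3: DE = 1.9, 1.96/√1.9 = 1.42, actual alpha = 15.5%.

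| m | ICC 0.1 | 0.2 | 0.3 | 0.5 | 0.7 |
|---|---|---|---|---|---|
| 2 (postpartum) | 6.2% | 7.4% | 8.6% | 11.0% | 13.3% |
| 3 | 7.4% | 9.8% | 12.1% | 16.6% | 20.6% |
| 4 | 8.6% | 12.1% | 15.5% | 21.5% | 26.6% |
| 5 | 9.8% | 14.4% | 18.6% | 25.8% | 31.5% |

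**Simulation on the visit schedule.** Beta-binomial data with no cohort difference, 200 against 100 women, 60% prevalence and 6,000 runs per cell. Entry was assumed uniform over 12 to 32 weeks, with delivery at 39 weeks (SD 1.8). Visits falling after delivery were not counted as pregnancy visits, although Section 6.2.1.2 moves Week 8 and 12 evaluations to the delivery visit in that case.

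| Rejection rate of the pooled test | ICC 0.1 | 0.2 | 0.3 | 0.5 | 0.7 |
|---|---|---|---|---|---|
| Pregnancy, Entry counted (mean 3.8 visits) | 8.4% | 11.4% | 15.9% | 21.0% | 26.9% |
| Pregnancy, Entry not counted (mean 2.8) | 7.4% | 9.5% | 12.4% | 16.3% | 20.3% |
| Postpartum, 2 visits | 6.0% | 7.4% | 9.7% | 11.0% | 13.9% |

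With Entry counted and prevalence at 90%, the rates are 8.5%, 12.5%, 15.4%, 21.2% and 26.0%, so the result hardly depends on the assumed 60%.

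**After the fix.** A cluster-robust test on the same data (GEE with independence working correlation and sandwich variance) rejects 4.7-5.9% of the time in pregnancy and 5.2-5.8% postpartum.

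**The case against.** The strongest reply is that the plan already contains the right analysis. The sentence after the chi-square evaluates the cohort association by GEE with confounder adjustment, and STI incidence is compared by Cox regression in the same paragraph. Cohorts are self-selected, and Section 9.2.1 says confounding will be handled in multivariable models. An unadjusted p-value is therefore weak ground for a conclusion about risk compensation, clustered or not. The objective is listed under Other, no decision rule hangs on it, and its detailed analysis is left to a later SAP.

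Most of this stands, and it limits the point. A reader might infer that the trial's answer on behavioral disinhibition rests on an invalid test. The documents do not support that, because the GEE and Cox analyses are planned for it.

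A reader might also take a fixed inflation of two to five times the nominal 5%. That is not supported either, since it depends on a correlation the documents do not give. The upper end (25.8/5 = 5.2) needs five pregnancy visits from every woman at ICC 0.5. The schedule simulation for ICC 0.2 to 0.5 reaches 9.5/5 = 1.9 to 21.0/5 = 4.2.

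The GEE does not remove the defect, however. The chi-square on visits is a separately stated between-cohort comparison, and no ranking of the analyses is given. The GEE sentence mentions no contrast by period, so as written the pregnancy and postpartum comparisons fall to the chi-square alone. A later SAP could correct this, but the protocol text stands until it does.

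**Conclusion.** The chi-square tests on the pregnancy and postpartum visit proportions are wrong as written. Their p-values are anti-conservative whenever reports from the same woman are positively correlated.

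The size depends on an assumed ICC. For 0.1 to 0.7, the formula gives a true alpha of about 7-32% with 3 to 5 pregnancy visits and about 6-13% with 2 postpartum visits. For 0.2 to 0.5, the pregnancy figure is about 10-26% by formula and about 9.5-21% in the schedule simulation, which also assumes entry and delivery timing. The protocol does not say whether the Entry report counts as during pregnancy; the simulation range covers both readings.

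The defect is confined to these unadjusted visit-level p-values. Severity: minor.

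**What to change.** In protocol Section 9.2.6 and in the separate SAP for other objectives:

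- Keep chi-square for the single-visit comparisons only.
- Report the pregnancy and postpartum visit proportions descriptively by cohort.
- Test them with period-specific cohort contrasts from the planned GEE (clustered on woman, robust variance), or with another cluster-adjusted test such as Rao-Scott.
- Name the GEE as the inferential analysis for sexual risk behavior.
- State whether the Entry report belongs to the pregnancy period.

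This takes a few sentences and no new data. The cost is wider intervals and fewer nominally significant results.

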Laboratory	
Collect blood for:
 

• HIV RNA test

• Store plasma for HIV drug resistance testing

• Rapid HIV test [see Section 6.3 in the event the test is (+)]

• Baseline TFV-DP level (DBS)

• Syphilis testing

• HSV2

 
Collect vaginal swab or urine for:
 

• Chlamydia and gonorrhea

 
Collect vaginal swab for:
 

• Microbiome

 
Collect rectal swab (if consented) for:
 

• Microbiome

Study Drug	
Cohort 1 only:
 

• Prescribe and dispense study drug

 A negative test result must be available prior to enrollment.

 Baseline sample must be collected prior to ingestion of study drug for Cohort 1 participants; the sample for Cohort 2 participants can be collected at any time and is required to confirm the participant is not receiving PrEP as standard of care.

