#### PrEP Comparison Component Maternal PP Week 26 Visit Procedures (Week 26 $\pm$ 14 days)

Behavioral and Counseling	
 
• iNSC [see Section 5.3.2]
 
• CASI and COVID-19 questionnaire [see Section 6.16]
 
• Qualitative IDI Visit [see Section 6.2.1.8]
 
• Assess for social harms [see Section 13.6]
 

Clinical	
 
• Obtain interim medical/medications history
 
• Perform targeted physical exam
 
• Identify/review/update adverse events
 
• Perform additional evaluations per Section 8 and/or if clinically indicated (consult CMC if indicated)
 

Laboratory	
Collect blood for:
 
 
• HIV RNA test
 
• Store plasma for HIV drug resistance testing
 
• Rapid test [see Section 6.3 in the event the test is (+)]
 
• ALT, Creatinine, and CrCl
 
• Hepatitis B surface antigen
 
• Syphilis testing
 
• HSV2
 
• Pregnancy testing (blood or urine test may be performed)
 
 
Cohort 1 and Cohort 2/Step 2 only:
 
 
• TFV-DP level (DBS)
 

PrEP Comparison Component Maternal PP Week 26 Visit Procedures (Week 26 ± 14 days)		
	Other	
Collect vaginal swab or urine for:
 
 
• Chlamydia and gonorrhea
 
 
Collect vaginal swab for:
 
 
• Microbiome
 
 
Collect rectal swabs (if consented) for:
 
 
• Microbiome
 
 
Cohort 1 and Cohort 2/Step 2 only:
 
 
• Collect vaginal secretions for drug level
 

	Urine	
 
• Pregnancy testing (blood or urine test may be performed)
 

	Other	
Radiology
 
DXA scan of:
 
 
• Hip
 
• Lumbar Spine
 
 
Note: Pregnancy test required within 14 days prior to DXA scan.

	Study Drug	
Cohort 1 and Cohort 2/Step 2 only:
 
 
• Collect study drug
 

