## 6.4.2 Early Study Discontinuation During the PrEP Comparison Component

### 6.4.2.1 Maternal Procedures at Early Study Discontinuation

PrEP Comparison Component Maternal Early Study Discontinuation Procedures		
Behavioral and Counseling		
 
• iNSC [see Section 5.3.2]
 
• Assess for social harms [see Section 13.6]
 

Clinical		
 
• Obtain interim medical/medications history
 
• Perform targeted physical exam
 
• Identify/review/update adverse events
 
• Perform additional evaluations per Section 8 and/or if clinically indicated (consult CMC if indicated)
 

Laboratory	Blood	
Collect blood for:
 
 
• HIV RNA test
 
• Plasma storage for resistance testing
 
• ALT, creatinine, and CrCl
 
• Rapid HIV test [see Section 6.3 in the event the test is (+)]
 
• Hepatitis B surface antigen
 
• Syphilis testing
 
• HSV2
 
• Pregnancy testing, as needed (blood or urine test may be performed)
 
 
Cohort 1 and Cohort 2/Step 2 only:
 
 
• TFV-DP level (DBS)
 
• 
 

	Other	
Collect vaginal swab or urine for:
 
 
• Chlamydia and gonorrhea
 
 
Collect vaginal swab for:
 
 
• Microbiome
 
 
Collect rectal swabs (if consented) for:
 
 
• Microbiome
 
 
Cohort 1 and Cohort 2/Step 2 only:
 
 
• Collect vaginal secretions for drug level
 

	Urine	
 
• Pregnancy testing, as needed (blood or urine test may be performed)
 

Other	Radiology	
DXA scan of:
 
 
• Hip
 
• Lumbar Spine
 
 
Note: Pregnancy test required within 14 days prior to DXA scan.

Study Drug		
Cohort 1 or Cohort 2/Step 2 only:
 
 
• Collect study drug
 

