**Table 6: Other Outcome Measures – PrEP Comparison Component**

Other Measures – PrEP Comparison Component	
Objective	Outcome Measure
2.4.1	PrEP adherence: TDF-DP drug concentration level in DBS
2.4.2	Sexual risk behavior 
 
Any condomless vaginal or anal sex
 
Incident sexually transmitted infection defined as any new HSV, syphilis, chlamydia or gonorrhea infections during follow-up
 
Incident HIV infection
 

2.4.3	
 
Antiretroviral drug resistance: presence of virus resistant to TDF at time of HIV diagnosis
 

2.4.4	Bone mineral density – Mean maternal bone mineral density (g/m  ) based on DXA scan of the lumbar spine (LS-BMD) and hip (H-BMD) at delivery and 26 weeks postpartum

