ALT, creatinine, CrCl	4mL		4mL		4mL	4mL	4mL	4mL		4mL	4mL	
Hepatitis B surface antigen	3mL										3mL	
Syphilis		1mL									1mL	
HSV2		1mL									1mL	
Glucose (random)	1mL											
Chlamydia/gonorrhea (vaginal swab or urine)		X									X	
Microbiome (rectal swabs); if consent provided		X			X  (EGA 34-38/40 weeks)				X		X	
Microbiome (vaginal swab)		X			X  (EGA 34-38/40 weeks)				X		X	
Vaginal secretion sampling for drug level					X  (EGA 34 -38/40 weeks)				X		X	
Urinalysis (protein and glucose)	X											
Ultrasound	X											
DXA scan (Hip, Lumbar Spine) 								X			X	
Pregnancy Test 										X	X	
Total maximum blood volume	15mL	12mL	14 mL	10mL	14mL	14mL	14mL	14mL	10mL	18mL 	20mL 	

 CASI is done at Week 26 visit only; CASI is not required at early D/C.

 If positive refer to [Section 6.3.1](#) and [Appendix IID](#) for additional procedures.

 Store plasma for HIV drug resistance testing at all visits indicated EXCEPT Screening.

 Blood collected for other tests will be used for the rapid HIV test; collection of additional blood is not required.

 Collect sample at any visit which occurs at an estimated 34 – 38/40 weeks' gestation.

 DXA scan at Wk 26/Exit and early D/C (as applicable) must be preceded by a pregnancy test.

 Urine (5mL) or blood (1mL) tests are acceptable. The total blood volume shown above accommodates collection of 1mL of blood, if needed. Note: *Pregnancy testing may be done prior to the DXA scan at Wk 26/Exit and Early D/C and does not need to be repeated.*

As per [Section 6.5](#)

## Appendix IIB (Schedule of Evaluations): Maternal PrEP Comparison Component Cohort 2

MATERNAL PROCEDURES:	SCR	Entry	Wk 4	Wk 8	Wk 12	Wk 24	Wk 36	L&D	PP Wk 6	PP Wk 14	PP Wk 26 / Exit and Early D/C	Step Change	
												Visit 1	Visit 2
Informed Consent	X												
Medical and Drug History	X	X	X	X	X	X	X	X	X	X	X	X	X
Physical Examination	X	X	X	X	X	X	X	X	X	X	X	X	X
Study drug dispensing													X
Assess for social harms			X	X	X	X	X	X	X	X	X	X	X
iNSC	X	X	X	X	X	X	X	X	X	X	X	X	X
CASI evaluations and COVID-19 questionannire		X	X	X	X	X	X			X	X 	X	X
Qualitative IDI							X				X		
HIV RNA  ; store plasma for HIV drug resistance testing 	4mL	6mL	6mL	6mL	6mL	6mL	6mL	6mL	6mL	6mL	6mL	6mL	
Rapid HIV 	X	X	X	X	X	X	X	X	X	X	X		X

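### STI incidence is to be compared by Cox regression separately before and after delivery, but routine STI tests fall only at entry and at exit, so for completers a screened infection cannot be assigned to either period

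*Protocol*

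**What the plan says.** Protocol Section 9.2.6 (Other Objective 2.4.2) says that "Cox regression methods will be used to estimate and compare the incidence rates of STIs in the antepartum period, the postpartum period"; a third comparison covers the whole of follow-up. The at-risk set is described as "among women with no STIs at enrollment in Cohort 1 and Cohort 2, adjusting for baseline confounders". Table 6 defines the endpoint as "any new HSV, syphilis, chlamydia or gonorrhea infections during follow-up"; incident HIV is a separate outcome with its own Cox analysis.

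The test schedule is as follows.

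- **Entry** (Section 6.2.1.1): "Syphilis testing", HSV2, and chlamydia and gonorrhea on a vaginal swab or urine.
- **Week 26 postpartum** (Section 6.2.1.7): the same set, including "Chlamydia and gonorrhea".
- **Early discontinuation** (Section 6.4.2.1): the same set, only for women who leave early.
- **Appendices IIA and IIB**: the STI rows are marked at Entry and in the combined Week 26/Exit and Early Discontinuation column, in both cohorts.

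No STI test is listed at antepartum Weeks 4, 8, 12, 24 or 36, at Labor and Delivery, at postpartum Weeks 6 or 14, or at the Step Change visits. Between the scheduled tests, Section 3.3 provides testing and syndromic treatment as needed. Section 6.8 requires new conditions, STIs included, to be recorded in the interval history, which may rest on self-report.

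**The concern.** A period-specific Cox model needs to know whether each infection arose before or after delivery and, within the period, when. The routine tests give a completer one follow-up result, about 26 weeks after delivery. A new positive shows only that infection occurred at some point since entry. The protocol names no method for interval-censored data and gives no rule for dating an infection found at exit.

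If such infections are dated at detection, the postpartum rate absorbs infections acquired in pregnancy, and the antepartum rate reflects mainly who had symptoms, sought care or reported a diagnosis. The two periods would then be measured by different processes, and a difference between them, or between cohorts within one of them, could not be read as a difference in STI incidence. On a clock running from entry, detection time would largely reflect gestational age at entry, which Section 9.2.5 itself names as a possible source of imbalance between these non-randomized cohorts.

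**Working it through.** The documents give no STI rate, event count or power figure, so there is no stated number to reproduce. The check compares the analysis text with the schedule and then sizes the consequence.

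**Step 1. Is delivery always inside the testing gap?** Inputs: eligibility up to 32 weeks' gestation (Section 4.2.1.2), the second test at 26 weeks postpartum, and delivery at 40 weeks (assumption).

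Gap = (40 − gestational age at entry) + 26 weeks. Antepartum share = (40 − gestational age at entry) / gap.

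| Entry (weeks) | Antepartum weeks | Gap (weeks) | Gap (months, ÷ 4.345) | Antepartum share |
|---|---|---|---|---|
| 32 | 8 | 34 | 7.8 | 8/34 = 24% |
| 26 | 14 | 40 | 9.2 | 14/40 = 35% |
| 20 | 20 | 46 | 10.6 | 20/46 = 43% |
| 14 | 26 | 52 | 12.0 | 26/52 = 50% |

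The range of 7.8 to 12.0 months agrees with the 7 to 12 months of follow-up in the protocol schema. The protocol sets no lower limit on gestational age at entry, so a woman entering before 14 weeks would have a share above 50%. In every row delivery lies between the two tests.

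**Step 2. Can one exit result separate the two periods?** With cumulative hazards H_AP and H_PP before and after delivery, and infection still detectable at exit,

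P(newly positive at Week 26) = 1 − exp(−(H_AP + H_PP)).

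Only the sum is identified. Take entry at 26 weeks (14 antepartum weeks = 14/52 = 0.269 years; 26 postpartum weeks = 0.5 years) and an assumed 15% newly positive. Then H_AP + H_PP = −ln(0.85) = 0.1625. These splits all give exactly 15%:

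| Share of hazard antepartum | Antepartum rate per 100 person-years | Postpartum rate per 100 person-years |
|---|---|---|
| 0 | 0 | 32.5 |
| 0.25 | 15.1 | 24.4 |
| 0.50 | 30.2 | 16.3 |
| 0.75 | 45.3 | 8.1 |
| 1 | 60.4 | 0 |

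The 15% is illustrative; other values change the scale but not the conclusion. At 5%, −ln(0.95) = 0.0513, and the extremes are 0/10.3 and 19.1/0. At 30%, −ln(0.70) = 0.3567, and they are 0/71.3 and 132.5/0.

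**Step 3. What does dating at detection give?** For these completers' screened infections, the antepartum rate is 0 and the postpartum rate is about 0.15/0.5 = 30 per 100 person-years, whichever row of the Step 2 table is true.

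**The case against.** The strongest reply has four parts.

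1. **Scheduled tests can fall antepartum.** Early discontinuation carries the same STI tests, and a woman may leave before delivery. This stands. A reader might infer that no scheduled test can ever yield an antepartum event; that holds only for completers. Women who leave early are a selected group and do not rescue the comparison.
2. **Some infections are dated.** The endpoint is any new infection during follow-up, as-needed testing is available, and the interval history asks about STIs, with medical records used where possible. This also stands. A reader might infer that infection times cannot be observed at all; the documents do not support that. Ascertainment between tests is incomplete and symptom-dependent, and could differ by cohort.
3. **The sentence also plans a whole-study comparison.** The schedule does support a cohort comparison over the whole of follow-up, once the time between tests is handled. A reader might infer that the entire STI analysis fails; it does not.
4. **Detail is left to a later plan.** SAP Section 1.1 assigns other objectives to a separate SAP, which may handle dating, and placing events at the exit test is a likely default rather than a stated rule. That is fair, but the commitment to separate period comparisons is already in the protocol, and no dating rule can recover information that was not collected.

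**Conclusion.** The point holds for infections first found by the scheduled exit tests. In completers these are interval-censored across delivery and cannot be assigned to a period, so the antepartum and postpartum Cox comparisons cannot be supported for them. Separating the periods would need strong modelling assumptions that the plan does not state, such as constant hazards unrelated to gestational age at entry.

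The antepartum share of the testing gap is 24% to 50% for entry at 32 down to 14 weeks, assuming delivery at 40 weeks. A reader might take this share as the fraction of screened infections that would be misallocated. That would also require a constant hazard and infections persisting undetected to Week 26. Some acquired in pregnancy may be treated or cleared earlier, so the true fraction is unknown.

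The problem does not reach the HIV analysis, because HIV is tested at every scheduled follow-up visit. Objective 2.4.2 is not primary, and no primary conclusion depends on it. The text should nevertheless be corrected, because following it would give misleading period-specific rates.

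**What to change.** In Section 9.2.6 and in the separate SAP for other objectives:

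- Drop the antepartum/postpartum Cox comparison for screened infections.
- Among women negative at entry, compare cohorts on infection detected by the exit test (Week 26 or Early Discontinuation). Use binary regression, or complementary log-log regression with log weeks from entry to that test as offset, and the planned baseline confounders. State that the offset assumes a constant hazard. Keep women negative for all four infections as the set for the composite; per-pathogen results can be added.
- State that an exit swab or urine result for chlamydia or gonorrhea may miss infections cleared or treated earlier, so it can understate cumulative incidence.
- Report clinically dated diagnoses by period descriptively only, labelled as symptom-driven or self-reported.

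The cost is wording in the protocol and in the later plan. No new samples or visits are needed. What is given up is a period-specific comparison of screened infections, which the present schedule cannot supply.
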